4.2 Pharmacokinetic Endpoints

The following pharmacokinetic endpoints will be evaluated:

• Serum trehalose concentration at the following time points: pre-dose, $60 (\pm 5)$ min after start of infusion (SOI), $120 (\pm 5)$ min after SOI, and $240 (\pm 5)$ min after SOI.

4.3 Safety Endpoints

The safety endpoints are the same as those described in the M-SAP with the addition of tabulations of adverse events and clinically significant ECG and lab abnormalities that occurred after crossover into the OLE period.

5. Measurement Definitions

5.1 ALSFRS-R

The definitions of ALSFRS-R scores are the same as described in the M-SAP with the clarification that scores will be considered missing in cases of item nonresponse. Pre-baseline slope in ALSFRS-R (delta-FRS) is defined as 48 minus the baseline ALSFRS-R total score then divided by the number of months from onset of symptomatic weakness to the Baseline Visit. The number of months will be calculated as the difference in days from onset of symptomatic weakness to the Baseline Visit multiplied by 12 / 365.25. The date of onset of symptomatic weakness will be imputed as the fifteenth day of a month if not specified more precisely.

5.2 SVC

The derivation of SVC percent-predicted of normal is the same as described in the M-SAP with age calculated as number of days from date of birth to the date of a given SVC assessment divided by 365.25 and with the following correspondence between self-identified race and race defined by the GLI classification:

Self-identified Race	GLI-defined Race
American Indian or Alaska Native	Mixed/Other
Asian	South East Asian
Black or African American	African American
Native Hawaiian or Other Pacific Islander	Mixed/Other
White	Caucasian
Unknown	Caucasian
Not reported	Caucasian
More than one race indicated	Mixed/Other

5.3 HHD and Grip Strength

The derivation of HHD upper and lower extremity scores and HHD0 are the same as described in the M-SAP with the revision that HHD0 is a composite endpoint with death or death equivalent, whichever occurs first.

A second HHD time-to-event endpoint is defined as the time from the Baseline Visit to the second post-baseline occurrence of a muscle with a strength recording of 0 among those muscles

Page 19 of 37

that were non-zero at baseline or time to death or death equivalent, whichever occurs first $(HHD0^2)$.

Time at risk for HHD0 and HHD0² will be censored at the last date that an HHD assessment was performed up to the end of the Week 24 Visit window.

5.4 Biofluid Biomarkers of Neurodegeneration

Blood biomarkers of neurodegeneration and neuromuscular degeneration will be assayed. These will include serum creatinine and serum and CSF neurofilament light chain (NfL). Serum creatinine will be assayed by the kinetic Jaffe method (test 001370, Labcorp, Burlington, NC). NfL will be assayed by single-molecule array (Simoa; Quanterix, Billerica, MA). Levels of serum and CSF NfL that are reported to be below the limit of quantitation will be imputed at the limit of quantitation. All serum NfL results that pass Quanterix quality control criteria will be analyzed for primary analyses using serum NfL, both as a baseline covariate and as an endpoint. A secondary analysis of serum NfL as an endpoint will exclude measured concentrations less than 4 ng/mL if they are less than 2% of the maximum measured concentration for a given participant. Levels of serum and CSF NfL will be log-transformed in all analyses.

5.5 ALSAQ-40

The description of the ALSAQ-40 instrument and item-level scores are the same as described in the M-SAP. Each of the five domains will be scored as the mean of all domain-specific items multiplied by 25 (range 0 to 100). An overall total score will be calculated as the mean of all 40 items multiplied by 25 (range 0 to 100; Jenkinson et al. 2003). Domain scores and the total score will be missing if more than 20% of the applicable items are missing; otherwise, item non-response will be mean-imputed from other completed items from the same assessment. Higher scores indicate worse quality of life.

5.6 CNS-BFS

The definition of CNS-BFS total score is the same as described in the M-SAP.

5.7 Survival

The primary definition of survival time is the same as described in the M-SAP with the clarifications that PAV is defined as more than 22 hours per day of noninvasive or invasive mechanical ventilation for more than seven consecutive days, that time at risk should not be censored at date of consent withdrawal, and that time at risk should be censored at date last known alive. The date of PAV initiation, where applicable, will be imputed as the fifteenth day of a month if not specified more precisely. Any participant on PAV at baseline will be censored at baseline. A secondary survival endpoint of death alone, independent of any death equivalent (including a death equivalent that occurs prior to baseline), is also defined and will be censored at the Week 24 Visit if completed or at the earlier of the end of the Week 24 Visit window or date last known alive if a Week 24 visit is not completed. An exploratory survival endpoint of death or death-equivalent will censor at the earlier of last known PAV-free or last known alive.

Time at risk for the composite endpoint of death or death equivalent and time at risk for the endpoint of death alone will be measured from each participant's Baseline Visit. Time at risk will be censored at two time points: (1) at the Week 24 Visit as defined in the M-SAP, and (2) at a

Page 20 of 37

subsequent assessment of death or death equivalent scheduled approximately at the end of placebo-controlled follow-up of the last RGE participant. The primary analysis of survival will evaluate PAV-free survival to the Week 24 Visit time point.

5.8 King's ALS Clinical Staging System

The King's ALS Clinical Staging System (Roche et al. 2012) is a 4-level ordinal scale with the first three levels indicating the number (1, 2, or 3) of distinct central nervous system regions (bulbar, upper limb, and lower limb) with neuromuscular dysfunction and levels 4a and 4b indicating nutritional or respiratory failure secondary to ALS, respectively.

Participants will be classified to King's stage 1, 2, 3, 4a, or 4b based on scores from ALSFRS-R assessments according to a published derivation (Balendra et al. 2014). Bulbar involvement is defined as a score less than 4 on any of the ALSFRS-R questions in the bulbar domain (questions 1, 2, and 3). Upper limb involvement is defined as a score less than 4 on either of the ALSFRS-R questions related to hand function (questions 4 and 5A). Lower limb involvement is defined as a score less than 4 on the ALSFRS-R question about walking (question 8). Nutritional failure is defined as responding that the participant uses gastrostomy for greater than 50% of their nutrition. Respiratory failure is defined as a score of 0 on the ALSFRS-R question addressing dyspnea (question 10 or R-1) or a score less than 4 on the ALSFRS-R question about use of mechanical ventilation (question 12 or R-3). Participants without evidence by ALSFRS-R scores of involvement of any of the three central nervous system regions will be scored as King's stage 1 due to their confirmed diagnosis with ALS. Participant may meet criteria for both King's stage 4a and 4b.

5.9 Hospitalization and Other Clinical Events

Times to the following clinically relevant events are defined:

- Time to first hospitalization due to a serious adverse event (SAE),
- Time to first hospitalization due to an ALS-related SAE,
- Time to first use of assisted ventilation,
- Time to first placement of a feeding tube,
- Time to King's stage 4a or 4b, and
- Time to first instance of hospitalization for an SAE, feeding tube placement, tracheostomy, initiation of PAV, or death.

Time at risk for each event will be measured from each participant's Baseline Visit. Time to first hospitalization excludes hospitalizations for elective procedures. ALS-related SAEs are those indicated as related to ALS disease progression by the site investigator. Participants who are already using assisted ventilation or have a feeding tube at the time of the Baseline Visit will be excluded from analysis of those endpoints. Death or death equivalent will be considered an outcome for each of the events listed, forming a composite endpoint.

Time at risk for these events will be censored at the Week 24 Visit, if completed, the date of consent withdrawal, if withdrawn, or the last date at which the status of each endpoint is known prior to the end of the Week 24 Visit window for participants lost to follow-up. Time to King's stage 4a or 4b is interval censored between ALSFRS-R assessments.

5.10 TRICALS Risk Profile

The Treatment Research Initiative to Cure ALS (TRICALS) Risk Profile is based on the the European Network for the Cure of ALS (ENCALS) survival prediction model (Westeneng et al. 2018). The TRICALS score will be calculated at baseline as follows:

Profile =
$$0.474[(VC/100)^{-1} + (VC/100)^{-1/2}] - 2.376[(DD/10)^{-1/2} + ln(DD/10)]$$

- $1.839(dFRS + 0.1)^{-1/2} - 0.264(AAO/100) + 0.271$ Bulbar
+ 0.238 Definite + 0.415 FTD

where *VC* is vital capacity in units of percent-predicted using GLI norms as defined in Section 5.2, *DD* is diagnostic delay calculated as (date of diagnosis – date of symptom onset) / 365.25 x 12, *dFRS* is pre-baseline slope of ALSFRS-R total score as defined in Section 5.1, *AAO* is age at symptom onset calculated as (date of symptom onset – date of birth) / 365.25, Bulbar is an indicator of initial site of onset in the bulbar region, Definite is an indicator for classification as definite ALS by revised El Escorial criteria, and FTD is an indicator for frontotemporal dementia. While participants are not evaluated for frontotemporal dementia at baseline, given that presence of dementia defined broadly is an exclusion criterion at screening, TRICALS scores will be calculated assuming that participants do not have frontotemporal dementia.

5.11 Pharmacodynamic Biomarkers

CSF LC3-II levels in samples collected at Baseline and Weeks 16 or 24 will be assayed. The method of analysis of CSF LC3-II will be specified once known. Levels of CSF LC3-II that are reported to be below the limit of quantitation will be imputed at the limit of quantitation. Levels of CSF LC3-II will be log-transformed in all analyses.

5.12 Clinical Safety Laboratory Tests

Clinical safety labs include hematology, blood chemistry panel, liver function tests, thyroid function, urinalysis, and pregnancy testing in women of childbearing potential as specified in Section 9.1.2 Clinical Safety Laboratory Tests of the Master Protocol:

- Hematology: hematocrit, hemoglobin, platelet count, red blood cell (RBC) count, mean
 corpuscular volume, mean corpuscular hemoglobin, mean corpuscular hemoglobin
 concentration, RBC distribution width (RDW), RBC morphology, white blood cell (WBC)
 count, and counts and percentages of basophils, eosinophils, lymphocytes, monocytes, and
 neutrophils;
- Blood chemistry panel: bicarbonate, chloride, potassium, sodium, calcium, magnesium, phosphate, blood urea nitrogen, creatinine, estimated glomerular filtration rate (eGFR) calculated using the Modification of Diet in Renal Disease (MDRD) four-variable equation, creatinine clearance calculated using the Cockcroft-Gault equation, glucose, and hemoglobin A1c;
- Liver function tests: alanine aminotransferase (ALT [SGPT]), aspartate aminotransferase (AST [SGOT]), alkaline phosphatase (ALP), albumin, total protein, total bilirubin (TBL);
- Thyroid function tests: thyroid-stimulating hormone (TSH);
- Urinalysis: clarity, color, specific gravity, pH, microalbumin, protein, glucose, ketones, bilirubin, urobilinogen, nitrite, leukocyte esterase, and blood; and

• Pregnancy: qualitative and quantitative serum human chorionic gonadotropin (hCG).

Clinical safety labs will also include derived measures of potential drug-induced liver injury (DILI), including those that potentially meet the Hy's law criteria, as distinct safety lab outcomes.

Three potential DILI criteria will be defined:

- ALT or AST >3x ULN with TBL >1.5x ULN
- AST or ALT >3x ULN with TBL >2x ULN
- AST or ALT >3x ULN with TBL >2x ULN and ALP <2x ULN (potential Hy's Law cases) where ULN is upper level of normal and all levels are measured on the same day.

6. Statistical Methodology

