## SCHEDULE OF ACTIVITIES – PLACEBO-CONTROLLED PERIOD

As per the Schedule of Activities (SOA) below, visits must occur every 4 weeks and will be clinic-, phone- or telemedicine based, as applicable. In this regimen, participants receive a weekly infusion of trehalose or matching placebo. The infusions are performed at each site for at least the first 4 weeks then participant may be permitted, based on safety and tolerability assessments, to have infusions administered at home. There is a maximum 24-week duration of placebo-controlled treatment for a Regimen.

Activity (page 1 of 2)	Master Protocol or Regimen-Specific	Master Protocol Screening 	Regimen Specific Screening 	Baseline 	Week 2 	Week 4	Week 8	Week 12 	Week 16 	Week 20 	Week 24 or Early Term. Visit	Follow-Up Safety Call 
		Clinic	Clinic	Clinic	Phone	Clinic	Clinic	Phone	Clinic	Phone	Clinic	Phone
		-42 to -1 Days 	-41 to 0 Day 	Day 0	Day 14 ±3	Day 28 ±7	Day 56 ±7	Day 84 ±3	Day 112 ±7	Day 140 ±3	Day 168 ±7	28 days after last dose ±3 days
Written Informed Consent 	Master	X	X									
Written Informed Consent - OLE	Master								X			
Inclusion/Exclusion Review	Master	X	X 									
ALS & Medical History	Master	X										
Demographics	Master	X										
Physical Examination	Master	X										
Neurological Exam	Master	X										
Vital Signs 	Master	X		X		X	X		X		X	
Vital signs associated with infusion 	Regimen				Weekly in conjunction with study drug administration from week 1 through week 24							
Slow Vital Capacity	Master	X 		X			X		X		X	
Muscle Strength Assessment	Master			X			X		X		X	
ALSFRS-R	Master	X		X		X	X	X	X	X	X	
ALSAQ-40	Regimen			X							X	
CNS Bulbar Function Scale	Regimen			X			X		X		X	
12-Lead ECG	Master	X									X	
Clinical Safety Labs 	Master	X		X		X	X		X		X	
Biomarker Blood Collection	Master			X			X		X		X	

Activity (page 1 of 2)	Master Protocol or Regimen-Specific	Master Protocol Screening 	Regimen Specific Screening 	Baseline 	Week 2 	Week 4	Week 8	Week 12 	Week 16 	Week 20 	Week 24 or Early Term. Visit	Follow-Up Safety Call 
		Clinic	Clinic	Clinic	Phone	Clinic	Clinic	Phone	Clinic	Phone	Clinic	Phone

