### *1.2.3 Clinical Experience*

Previous clinical trials evaluating IV trehalose in healthy subjects and patients with OMPD and SCA3 are summarized below. Overall, administration of IV trehalose to adults appears safe and well tolerated.

A total of 59 subjects have been exposed to trehalose: 18 healthy subjects, 25 OMPD patients, 15 SCA3 patients, 1 adult with Sanfilippo Type B. Out of the 59, 11 patients received SLS-005 in the under expanded access use programs (10 subjects with OMPD and 1 with Sanfilippo type B). The healthy subjects received a single dose of 27, 54, or 81 g (6 subjects each dose), the OMPD patients received repeated weekly doses of 27 g trehalose for a duration of 6 to 18 months, the

SCA3 patients received repeated weekly doses of 13.5 or 27 g for a duration of 6 to 12 months, and the Sanfilippo patient is receiving 0.75 g/kg weekly, currently at over 4 months of treatment. Overall, trehalose was well tolerated.

Study BB-TRE-101 studied the safety, tolerability, and pharmacokinetics (PK) of single ascending doses of SLS-005 in healthy subjects. The study demonstrated proportional linear kinetics for increasing doses of trehalose from 27 g to 81 g. In addition, it demonstrated a need for weight-based dosing since clearance increased with increasing weight. One (1) treatment-emergent adverse event was assessed as possibly related elevated liver enzymes in 1 subject in the 81 g treatment group and was reported as a suspected unexpected serious adverse reaction (SUSAR). Based on the data from this study, along with supportive data from animal studies, the MTD was established as 0.75 g/kg.

Study BBCO-001, an open-label study in patients with OPMD, assessed the safety, tolerability, PK, and efficacy of SLS-005 in patients treated for 6 months with weekly infusions of 27 grams. SLS-005 was generally safe and well tolerated. The most common adverse event (AE) was elevated urine glucose that occurred in 52% of patients. The AE of glycosuria was only reported from 1 site and, although the patients were asymptomatic, the investigator assessed the laboratory result as clinically significant. Increased glucose in urine is an anticipated result because trehalose is metabolized to glucose, however serum glucose did not exceed normal range. There were 3 serious adverse events (SAEs) occurring in 2 patients: urinary tract infection, aspiration pneumonia, and aspiration leading to death. None of the SAEs were considered related to study drug.

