## 5.9 Overdose

Certain safety events that occur in association with investigational product may require reporting. These safety events include, but are not limited to, the following:

- Overdose of the investigational product, where ‘overdose’ is defined as  $> 125\%$  of the intended dose for a single treatment day infusion.
- Suspected abuse/misuse of the investigational product
- Inadvertent or accidental exposure to the investigational product
- Medication error involving study drug (with or without participant exposure to the investigational product, e.g., name confusion)
- The half-life of Trehalose Injection 90.5 mg/mL is approximately 1.5 hours, and there is no antidote. Trehalose is metabolized to 2 glucose molecules, there are no other metabolites. Supportive care with monitoring of vital signs, blood glucose levels, and liver enzymes should be considered. In 1 subject who received 81 g of Trehalose Injection 90.5 mg/mL, there was an increase in liver enzyme levels, but liver function remained normal and liver enzyme values returned to normal without treatment.

These safety events should be reported to the Coordination Center whether they result in an AE/SAE or not. Safety events associated with an AE/SAE should also be reported in the EDC. The SI should also contact the Medical Monitor within 24 hours of the SI’s awareness.

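### The liver-injury criteria in SAP 5.12 count only same-day abnormalities, so enzyme and bilirubin elevations found at different draws are never paired

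*SAP*

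**What the plan says.** SAP 5.12 adds derived measures of potential DILI to the clinical safety labs, to be reported "as distinct safety lab outcomes". There are three:

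- Row 1: "ALT or AST >3x ULN with TBL >1.5x ULN".
- Row 2: the same enzyme limit, with the bilirubin limit raised to 2x ULN.
- Row 3: row 2 plus ALP below 2x ULN, labelled as potential Hy's Law cases.

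The list ends with "where ULN is upper level of normal and all levels are measured on the same day".

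In the Protocol's Schedule of Activities for the placebo-controlled period, the row "Clinical Safety Labs" is marked post-baseline at Weeks 4, 8, 16 and 24 (Days 28, 56, 112 and 168, each ±7 days).

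SAP 6.6.2 follows the Master SAP for lab summaries with three changes. Results beyond 28 days after the last dose are not tabulated. Abnormal values are graded by CTCAE. The worst post-baseline grade is added to the shift tables.

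On prior experience, Protocol 1.2.3 reports "possibly related elevated liver enzymes in 1 subject in the 81 g treatment group", notified as a suspected unexpected serious adverse reaction. Protocol 5.9 (Overdose) adds that "liver function remained normal and liver enzyme values returned to normal without treatment".

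**The concern.** The three rows are the only place in the supplied documents where an enzyme result and a bilirubin result are combined within one participant. The same-day condition makes that combination depend on a single blood draw showing both abnormalities. If bilirubin rises after the enzymes have started to fall, the two may be recorded at different draws. With up to 56 days nominally between scheduled draws, the enzymes may be back at or below 3x ULN when the raised bilirubin is seen. The participant then appears in none of the rows.

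The bilirubin lag is general clinical reasoning and is taken here as an assumption; neither document describes it. At stake is how the table is read. A zero in the potential Hy's Law row will be taken to mean that no participant crossed both limits, whereas it would mean only that no participant crossed both on one day.

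**Working it through.** The plan states no figure on this point to reproduce, so the check is one of logic and timing.

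**Scope of the clause.** It follows the third bullet in the extracted text. It also defines ULN, which all three rows use, and it speaks of all levels, so it reads most naturally as covering all three. If it covered only the third, the first two would have no timing rule, which would also need clarifying.

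**Condition for a miss.** Write E for the higher of ALT and AST, and B for total bilirubin, both in multiples of ULN.

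- Row 1 is met if E > 3 and B > 1.5 on some day. Row 2 needs E > 3 and B > 2. Row 3 also needs ALP < 2.
- Row 3 lies within row 2, and row 2 within row 1. A participant meets none of them exactly when E ≤ 3 on every sampled day with B > 1.5.
- If bilirubin is between 1.5x and 2x ULN while E > 3, and exceeds 2x only once E ≤ 3, row 1 catches the participant but rows 2 and 3 do not.

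**Gaps between scheduled post-baseline draws** (Days 28, 56, 112, 168). With ±7 days at each end, the range is the nominal gap ±14.

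| Pair | Nominal gap | With visit windows |
|---|---|---|
| Week 4 to 8 | 56 − 28 = 28 days | 14 to 42 days |
| Week 8 to 16 | 112 − 56 = 56 days | 42 to 70 days |
| Week 16 to 24 | 168 − 112 = 56 days | 42 to 70 days |

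**Assumed lab courses.** The values are illustrative, in multiples of ULN, written as ALT / bilirubin. ALP is 1 throughout and the remaining draws are unremarkable. The two alternative pairings use the 2x bilirubin limit.

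| Course | Draws | Same-day rows | Bilirubin within 30 days after | Bilirubin at any later draw |
|---|---|---|---|---|
| (a) Concurrent | Day 56: 6 / 2.5 | all three met | flagged | flagged |
| (b) Enzymes falling, still above 3 | Day 28: 8 / 1.2; Day 56: 3.5 / 2.5 | all three met | flagged | flagged |
| (c) Enzymes at or below 3 by the next draw | Day 28: 8 / 1.2; Day 56: 2.5 / 2.5 | none met | flagged | flagged |
| (d) As (c), across the longer gap | Day 56: 8 / 1.2; Day 112: 2.0 / 2.5 | none met | not flagged | flagged |

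Courses (a) and (b) show that the rule works whenever the enzymes are still above 3x ULN at the draw with raised bilirubin. Courses (c) and (d) show the gap. Course (d) also shows that a 30-day look-forward would not close it: it cannot pair scheduled draws after Week 8 (at least 42 days apart) and can fail between Weeks 4 and 8 (up to 42 days).

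**Other outputs.** The SAP 6.6.2 shift tables would show a high enzyme grade and a high bilirubin grade, but separately by test. The safety endpoints in Protocol 2.1 include adverse events and clinically significant lab abnormalities, but no rule there links the two tests in one participant.

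**The case against.** The strongest reply is that these are descriptive derived outcomes and that a missed pairing hides no data. The individual values still reach the CTCAE grading and the worst-grade shift tables, and clinically significant abnormalities, adverse events and serious adverse events are safety endpoints in their own right. Row 1, with its lower bilirubin limit, already widens the net. This stands, and it limits the point to a gap in one derivation. A reader might infer that the rows are the trial's screen for serious liver injury; the documents do not give them that role.

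The Master SAP and Master Protocol may contain a paired display or liver follow-up rules. That cannot be checked. SAP section 1 ranks the regimen SAP above the Master SAP where they conflict, so a different timing rule for these same criteria would yield to 5.12. An additional display in the Master SAP would not conflict and could already close the gap.

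Two stronger readings are tempting. One is that the earlier liver event makes a missed case likely here, particularly as the heaviest eligible participants receive more than 81 g (144 kg × 0.75 g/kg = 108 g). In that event liver function stayed normal and the enzymes resolved, so it is background and not an example of delayed bilirubin. Protocol 1.2.3 and 1.3.2 also say that clearance rises with body weight, so equal grams are not shown to mean equal exposure. The other is to put a size on the risk from an assumed rate of enzyme decline and an early recheck. The documents give no enzyme kinetics and no recheck rule, and infusions continue weekly, so such a figure would rest on assumptions alone.

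**Conclusion.** The gap is real and narrow. As written, SAP 5.12 leaves out of all three rows any participant whose enzymes exceed 3x ULN at one draw but are at or below 3x ULN at every draw with bilirubin above 1.5x ULN. Nominal gaps of 28, 56 and 56 days between scheduled draws make this possible, and no other output in the supplied documents would identify the participant as having crossed both limits.

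The frequency cannot be estimated from the documents. The consequence is a possibly misleading zero, or a count that is too low, in a descriptive safety table. Efficacy analyses are unaffected and no safety analysis is invalidated. The conclusion rests on reading the same-day clause as covering all three rows and on the absence of a paired display in the Master SAP. It is a cheap improvement worth making.

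**What to change.** In SAP 5.12, keep the three same-day rows and add a non-concurrent row to each:

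- Peak ALT or AST above 3x ULN at any post-baseline draw, with total bilirubin above that row's limit on the same day or at any later post-baseline draw.
- For the third row, ALP below 2x ULN at the draw with the enzyme elevation.
- Draws limited to 28 days after the last dose, to agree with SAP 6.6.2.
- A listing of dates and values of ALT, AST, total bilirubin and ALP for every participant flagged, so that reviewers can judge whether two distant results belong together.

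The any-later-draw pairing is preferable to a fixed 30-day window, which cannot link consecutive scheduled draws after Week 8 and runs past the 28-day post-dose limit.

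The cost is a few lines of SAP text, a small derivation applied identically to both arms, and one listing. No samples or visits are added. The downside is a few more non-specific pairs to review, since an enzyme rise and an unrelated later bilirubin rise will also be flagged. Reporting the two sets of rows separately keeps the same-day count readable on its own.
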